2.8.1.1 Adverse events of special interest / grouping of AEs

The following Safety Topic of Interest will be used to define adverse events of special interest (AESI):

- Major adverse cardiovascular events (MACE): identified per Novartis MedDRA Query (NMQ) “MACE (MI, Stroke, Cardiovascular death)”
- Inflammatory bowel disease: identified per NMQ “Inflammatory bowel disease”
- Infections and Infestations: identified per SOC “Infections and infestations”
- Malignancy: identified per NMQ “Malignant or unspecified tumors “
- Hypersensitivity and injection site reaction: identified per SMQ (Standardized MedDRA Query) “Hypersensitivity”

For “Infections and infestations” , please follow below table:

Safety Topic Of Interest (AESI)	SOC	Data Domain	MedDRA Code	MedDRA Term	MedDRA A Level	MedDRA Qualifier
Tinea pedis	Infections and infestations	MEDDRA	10043873	Tinea pedis	PT	
Oral herpes	Infections and infestations	MEDDRA	10067152	Oral herpes	PT	
Oral candidiasis	Infections and infestations	MEDDRA	10030963	Oral candidiasis	PT	
Infections (Staphylococcal)	Infections and infestations	MEDDRA	10041925	Staphylococcal infections	HLT	
Infections (Skin structure)	Infections and infestations	MEDDRA	90000542	Infections of skin structures [STANDARD] (NMQ)	NMQ1	
Infections (Oesophageal candidiasis) (narrow)	Infections and infestations	MEDDRA	90000882	Oesophageal candidiasis	NMQ1	NARROW

				[STANDARD] (NMQ)		
Infections (Mycobacterial)	Infections and infestations	MEDDRA	10028440	Mycobacterial infectious disorders	HLGT	
Infections (Herpes viral)	Infections and infestations	MEDDRA	10019972	Herpes viral infections	HLT	
Infections (Fungal)	Infections and infestations	MEDDRA	10017528	Fungal infectious disorders	HLGT	
Infections (Central nervous system infections and inflammations)	Infections and infestations	MEDDRA	10007951	Central nervous system infections and inflammations	HLGT	
Infections (Opportunistic)	Infections and infestations	MEDDRA	90000701	Opportunistic infections [FINGOLIMOD (CMQ)]	NMQ1	
Infections (Oesophageal candidiasis) (broad)	Infections and infestations	MEDDRA	90000882	Oesophageal candidiasis [STANDARD] (NMQ)	NMQ1	BROAD
Infections (Infectious pneumonia)	Infections and infestations	MEDDRA	90000161	Infectious pneumonia [STANDARD] (NMQ)	NMQ1	BROAD
Infections	Infections and infestations	MEDDRA	10021881	Infections and infestations	SOC	
Candida infections	Infections and infestations	MEDDRA	10007134	Candida infections	HLT	

Above AESI will be considered and the number of patients with at least one event in each AESI grouping will be reported. Such AESI grouping consist of adverse events, for which there is a specific clinical interest in connection with secukinumab, or adverse events, which are similar in nature (although not identical).

All AESI groupings are defined through the use of PT, high level terms (HLT), SOC, SMQ, NMQ or through a combination of these components.

The AESI search table will be used to map reported adverse events to the notable adverse events groupings. The list of adverse events of special interest may be updated during the course of the trial based on accumulating safety data. Therefore, the clinical study report will list the AE groupings used and provide a listing of the corresponding AESI search table.

The crude rates of adverse events of special interest will be summarized by primary system organ class and preferred term.

In addition, exposure time-adjusted incidence rates including 95% confidence intervals will be provided for the entire treatment period at the preferred term level to adjust for differences in exposure. A graphical display of the crude rates and exposure-adjusted incidence rates will be presented for all AESIs by SOC.

Note that certain adverse events may be reported within multiple groupings.

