### **3.7 Risks and benefits**

As of June 2016, approximately 16,400 patients and healthy subjects have been enrolled in both completed and ongoing studies with secukinumab, with over 14000 having received secukinumab at doses ranging from single and multiple i.v. doses of 0.1 mg/kg up to 30 mg/kg and s.c. doses of 25 mg up to 300 mg across various indications including AS, psoriasis, rheumatoid arthritis, PsA, multiple sclerosis, uveitis, dry eye, Crohn's disease, asthma and polymyalgia rheumatica.

The risk profile of secukinumab in axSpA is informed by the safety data from the pivotal clinical trials in moderate to severe plaque psoriasis and the spondyloarthritides (e.g. PsA and AS). For these indications, secukinumab has shown a higher rate of total adverse events (AEs), mainly infections, when compared to placebo (placebo-controlled periods of 12 to 16 weeks depending on the protocol). The majority of infections were non-serious upper respiratory tract infections. However, no clinically meaningful difference was observed in infectious serious adverse events (SAEs). In addition, no dose dependency with secukinumab (300 mg and 150 mg) was observed in the overall rate of infections or upper respiratory tract infections.

Adverse drug reactions (ADRs) classified as very common ( $\geq 1/10$  patients) or common ( $\geq 1/100$  but  $< 1/10$  patients) included upper respiratory tract infections (nasopharyngitis, upper respiratory tract infection, rhinitis and pharyngitis), oral herpes, rhinorrhea, diarrhea and urticaria. Uncommon ( $\geq 1/1000$  but  $< 1/100$  patients) ADRs included sinusitis, tonsillitis, oral candidiasis, tinea pedis, neutropenia and conjunctivitis.

Infections, neutropenia and hypersensitivity are important identified risks, while malignancies, major adverse cardiovascular events, immunogenicity, Crohn's disease, and hepatitis B

reactivation (Europe only) are important potential risks. Interaction with live vaccines is an important potential risk.

Immunogenicity was low with secukinumab and did not correlate with loss of efficacy in all indications studied to date.

From the standpoint of the overall risk benefit assessment, the current trial with secukinumab is justified.

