## 13 Appendices

### 13.1 Appendix 1: Clinically notable laboratory values

The following criteria included in [Table 13-1](#) will be used to define expanded limits and notable abnormalities of key laboratory tests.

Clinically notable values will be forwarded to Novartis at the same time that they are sent to investigators. Any action based on these laboratory values should be discussed with Novartis personnel.

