2.8.3 Laboratory data

The summary of laboratory evaluations will be presented for three groups of laboratory tests (hematology, chemistry and urinalysis).

For urinalysis, only data listing will be presented.

Descriptive summary statistics for the change from baseline to each study visit will be presented. These descriptive summaries will be presented by laboratory test and treatment group. Change from baseline will only be summarized for patients with both baseline and post baseline values and will be calculated as:

$$\text{change from baseline} = \text{post baseline value} - \text{baseline value}$$

For each parameter, the maximum change from baseline within each study period will be analyzed analogously.

Table 2.8-1 Liver-related events

Parameter	Criterion
ALT	>3xULN; >5xULN; >8xULN; >10xULN, >20xULN
AST	>3xULN; >5xULN; >8xULN >10xULN; >20xULN
ALT or AST	>3xULN; >5xULN; >8xULN >10xULN; >20xULN
TBL	>1.5xULN, >2xULN, >3xULN,
ALP	>2xULN, >3xULN. >5xULN
ALT or AST & TBL	ALT or AST >3xULN & TBL >2xULN; ALT or AST >5xULN & TBL >2xULN; ALT or AST >8xULN & TBL >2xULN; ALT or AST >10xULN & TBL >2xULN
ALP & TBL	ALP >3xULN & TBL >2xULN ALP >5xULN & TBL >2xULN
ALT or AST & TBL & ALP	ALT or AST >3xULN & TBL >2xULN & ALP <2xULN (Hy's Law) Note: elevated ALP may suggest obstruction as a consequence of gall bladder or bile duct disease; ALP may also be increased in malignancy. FDA therefore terms Hy's Law cases as indicators of pure hepatocellular injury. This does not mean that cases of ALT or AST >3xULN & TBL >2xULN & ALP \geq 2xULN may not result in severe DILI.

Notes:

In studies which enroll patients with pre-existing liver disease, baseline LFT may be increased above

ULN; in such a case it is meaningful to add the condition “and worse than baseline” to the abnormality Criteria

For a combined criterion to be fulfilled, all conditions have to be fulfilled on the same visit. The criteria are not mutually exclusive, e.g. a subject with ALT = 6.42xULN is counted for ALT >3xULN and ALT>5x ULN.

Individual subject data listings will be provided for patients with abnormal laboratory data. Data of patients with newly occurring or worsening liver enzyme abnormalities will be listed in an additional listing.

Separate summaries and listings will be provided for urine pregnancy results by visit for each treatment period.

Listing will be provided for all renal events captured in the study.

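### Neutropenia is the only one of the protocol's three important identified risks without an AESI grouping, and the notable haematology limits in Protocol Table 13-1 are never counted by arm

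*SAP*

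**What the plan says.** **Risk statement.** Protocol 3.7 states: "Infections, neutropenia and hypersensitivity are important identified risks". It places neutropenia in the uncommon class (at least 1/1000 but below 1/100): "ADRs included sinusitis, tonsillitis, oral candidiasis, tinea pedis, neutropenia and conjunctivitis".

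**AESI list.** SAP 2.8.1.1 begins: "The following Safety Topic of Interest will be used to define adverse events of special interest (AESI". Five topics follow. Two of them match identified risks: "Infections and Infestations: identified per SOC" and "Hypersensitivity and injection site reaction: identified per SMQ". The others are MACE, inflammatory bowel disease and malignancy. The detailed search table in that section covers infections only. For each AESI the SAP plans a patient count per grouping, crude rates, and exposure-adjusted rates with 95% CIs at preferred-term level, with no frequency cut. The section adds: "The list of adverse events of special interest may be updated during the course of the trial based on accumulating safety data".

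**Other adverse events.** SAP 2.8.1 tabulates all treatment-emergent events by treatment, system organ class and preferred term. It limits preferred-term exposure-adjusted rates to SAEs and to events with a frequency above 2%.

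**Laboratory data.** Protocol Appendix 1 says that the criteria in Table 13-1, a table titled for safety analyses, "will be used to define expanded limits and notable abnormalities of key laboratory tests". For haematology they are neutrophils below 0.9 x LLN, WBC below 0.8 x LLN, platelets below 100 x 10^9/L, and a 20 g/L fall in haemoglobin from Baseline. SAP 2.8.3 gives haematology change from baseline by visit, maximum change within each period, and patient listings of abnormal values. Its only threshold table is "Table 2.8-1 Liver-related events". SAP 2.8.4.2 does plan the number and percentage of patients with newly occurring notable vital signs.

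**The concern.** There are two separate gaps.

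First, the SAP describes its AESI groupings as events of specific clinical interest in connection with secukinumab. An important identified risk meets that description, yet only two of the three are grouped. Rarity does not explain the choice: oral candidiasis and tinea pedis share neutropenia's frequency class in Protocol 3.7, and each has its own row in the AESI search table.

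Second, the adverse event tables depend on what the investigator reports. Under Protocol 7.1 an abnormal laboratory value becomes an AE only if it produces signs or symptoms, is judged clinically significant, or needs therapy. A neutrophil count below the Table 13-1 limit that meets none of these is not an AE. It can then be identified as a notable value only in a patient listing, because a summary of change does not say whether a limit was crossed.

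At stake is how clearly the report describes an identified risk on 150 mg against placebo in Period 1, and on 300 mg against 150 mg in Period 2. Protocol 1.2 includes the safety of both comparisons in the study's purpose.

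**Working it through.** The plan states no figure on this point, so there is none to reproduce. The check is a cross-reading of the documents plus one calculation on the 2% rule.

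**Step 1: identified risks against AESI topics.**

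| Important identified risk (Protocol 3.7) | Topic in SAP 2.8.1.1 |
|---|---|
| Infections | Yes, whole SOC plus sub-table |
| Hypersensitivity | Yes, by SMQ |
| Neutropenia | No |

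The SAP mentions neutrophils only once, in deviation EXCL17 (SAP 5.5), which concerns screening eligibility and not safety analysis.

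**Step 2: would reported neutropenia reach the exposure-adjusted table without AESI status?** Inputs: frequency p from 0.001 to 0.01 (Protocol 3.7), with 0.005 as an intermediate value chosen here; group sizes 264, 88 and 352 (SAP section 3); cut above 2% (SAP 2.8.1). The SAP does not say in which denominator the 2% is taken, so three are shown.

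- Expected cases = N x p.
- Smallest count above 2%: r = floor(0.02 x N) + 1. For 264: 5.28, so r = 6. For 352: 7.04, so r = 8. For 88: 1.76, so r = 2.
- Chance of passing the cut = P(X >= r), with X binomial(N, p).

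| N | r | Expected at 0.1% / 0.5% / 1% | P(X >= r) at 0.1% / 0.5% / 1% |
|---|---|---|---|
| 264 (150 mg) | 6 | 0.26 / 1.32 / 2.64 | <0.0001 / 0.0023 / 0.051 |
| 352 (all) | 8 | 0.35 / 1.76 / 3.52 | <0.0001 / 0.0005 / 0.027 |
| 88 (placebo origin) | 2 | 0.09 / 0.44 / 0.88 | 0.0036 / 0.072 / 0.22 |

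For the 264, the chance of at least one case is 0.23 at 0.1% and 0.93 at 1%. At the upper end a case is likely to occur, yet the event is unlikely to pass the 2% cut. As an AESI it would get the exposure-adjusted rate regardless.

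**Step 3: what is counted against a threshold.**

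| Data | Limits defined | Planned by-arm threshold analysis |
|---|---|---|
| Vital signs | SAP Table 2.8-2 | Yes, n and % newly occurring |
| Liver tests | SAP Table 2.8-1 | Yes, with a rule for counting patients |
| Haematology | Protocol Table 13-1 | None; change, maximum change, listings |

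Threshold counts are therefore already part of the SAP's approach. Haematology, which holds the laboratory measure of an identified risk, is outside it.

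**The case against.** The strongest reply is that neutropenia is not neglected. Several parts of it stand.

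- **A reader might infer that neutropenia gets no rate at all.** The documents do not support that. SAP 2.8.1 gives every treatment-emergent event a crude by-arm rate by system organ class and preferred term, at any frequency. Serious cases also get exposure-adjusted rates.
- **A reader might infer that the laboratory plan would hide individual falls in the neutrophil count.** SAP 2.1 includes minimum, quartiles and maximum among the summaries for continuous variables, and SAP 2.8.3 adds maximum change and listings. A large fall would probably be visible. The number of patients below the protocol's limit in each arm would not.
- **A reader might infer that the SAP contradicts its own section 4, which declares no change to protocol analyses.** It does not. Protocol 9.5.2.2 also plans only change and maximum change, and Protocol section 9 never calls for a count from Table 13-1. Elsewhere the protocol uses Appendix 1 as guidance on discontinuation, for alert ranges and for forwarding values to the sponsor.
- **A reader might infer that the AESI list otherwise matches the protocol's risk list.** It does not: immunogenicity, hepatitis B reactivation and live-vaccine interaction, all named as potential risks, have no topic either. Neutropenia stands alone only among the three identified risks.
- **Small numbers.** Assuming 1:1 re-randomization (the ratio is not stated) and the planned non-response of 1 - 0.436 = 0.564, Arm A3 would have 264 x 0.564 / 2 = about 74 patients and Arm B2 88 / 2 = 44. At 1% that is about 0.7 and 0.4 events. No dose comparison can rest on such counts. This limits what the added output can show, but does not argue against reporting it.
- **The AESI list may be updated.** That permits the addition without committing to it, and neutropenia was already a known risk when the protocol was written.

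**Conclusion.** The point holds as a limited reporting gap in two parts. Reported non-serious neutropenia at or below 2% gets a crude rate, but no grouped AESI count and no preferred-term exposure-adjusted rate with CI. Notable haematology values are never counted by arm, so low counts that are not AEs can be identified only in listings.

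The size is small: 0.26 to 2.64 expected cases among 264 patients, with a chance of at most about 0.05 of passing the 2% cut in that group (0.03 over all 352; up to 0.22 if the cut is taken within the 88). This assumes that the frequency class in Protocol 3.7 applies to this population and duration. The documents give no frequency for neutrophil counts below 0.9 x LLN, so the size of the laboratory gap cannot be stated.

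The two parts need separate remedies. A reader might infer that an AESI row would also capture low counts that were never reported. It would not, because SAP 2.8.1.1 maps reported adverse events to its groupings; only the laboratory table addresses those counts. The primary and secondary efficacy analyses are unaffected.

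**What to change.** 1. **SAP 2.8.1.1:** add neutropenia as an AESI grouping and state its search terms, so that it gets the same counts, crude rates and exposure-adjusted rates as the other topics.

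2. **SAP 2.8.3:** add a table of n (%) of patients, by arm and period, with newly occurring Table 13-1 haematology abnormalities, defined as follows.
   - Neutrophils, WBC and platelets: the criterion was not met at study baseline and, for Period 2, was also not met at any earlier post-baseline assessment. The second condition is needed because SAP 2.1.1 makes Week 8 the baseline for Period 2; without it, an abnormality that began in Period 1 could be counted again as new.
   - Haemoglobin: a first decrease of at least 20 g/L from the baseline before the first dose. This criterion is itself a change, so a rule that it was not met at baseline has no meaning.
   - Week 8 samples belong to Period 1, as SAP 2.1.1 already provides for assessments.

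**Cost:** one extra row in the search table and one extra output. Haematology is already scheduled in both periods (Protocol Table 6-1), so no new data are needed. The counts will be small and should be presented as descriptive, without tests between arms.

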**Table 6-1 Assessment schedule**

	Screening	Treatment Period 1 Double-blind placebo-controlled (last dose at Week 4)					Treatment Period 2 Double-blind active (last dose at Week 20)				USV**	Comments
Visit number	1	2	3	4	5	6	7	8	9	10 EOS/ PPD*		* EOS/PPD - Patients who prematurely discontinue during the treatment period should return for assessments associated with the Week 24 visit (i.e. 4 weeks after the last study treatment). ** Unscheduled visit – assessments at the discretion of the investigator.
Week	-10 to -1	0	1	2	3	4	8	12	20	24		
Recommended visit window (days)			± 2	± 2	± 2	± 2	± 2	± 5	± 5	± 5		
Information and informed consent	X											
Inclusion & exclusion criteria	X	X										
axSpA history		X										
Spinal pain responder assessment							X					
Demographics	X											
Relevant medical history/ current medical conditions	X											
Prior medication/ concomitant medication	X	X	X	X	X	X	X	X	X	X	X	
AEs/ SAEs (including injection site reactions)	X	X	X	X	X	X	X	X	X	X	X	AEs/SAEs occurring after the patient has signed the informed consent (including those that occur during home administration of study drug) must be captured on the appropriate eCRF page. Any AEs that are treatment-emergent should be reported until 12 weeks after the last study treatment.

	Screening	Treatment Period 1 Double-blind placebo-controlled (last dose at Week 4)					Treatment Period 2 Double-blind active (last dose at Week 20)					USV**	Comments
		1	2	3	4	5	6	7	8	9	10 EOS/ PPD*		
Visit number	1	2	3	4	5	6	7	8	9	10 EOS/ PPD*			* EOS/PPD - Patients who prematurely discontinue during the treatment period should return for assessments associated with the Week 24 visit (i.e. 4 weeks after the last study treatment). ** Unscheduled visit – assessments at the discretion of the investigator.
Week	-10 to -1	0	1	2	3	4	8	12	20	24			
Recommended visit window (days)			± 2	± 5	± 5	± 5							
Smoking history		X											
Cardiovascular medical history	X												
Physical examination	S	S	S	S	S	S	S	S	S	S	S		
Height† and weight		X								X	X		† Height will be assessed at Visit 2 or unscheduled visit only.
Vital signs	X	X	X	X	X	X	X	X	X	X	X		
QuantIFERON TB-Gold test	X											X	

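### The SAP names injection site reactions as part of an AESI topic but gives them no search of their own, and pools any that are captured with hypersensitivity

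*SAP*

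**What the plan says.** SAP 2.8.1.1 lists five safety topics. The last is "Hypersensitivity and injection site reaction: identified per SMQ", and the only query named is the standardized MedDRA query for hypersensitivity. The bullet gives no narrow or broad scope.

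A search table comes next, but it serves the infections topic only ("please follow below table"). It has no row for hypersensitivity or for injection site reactions, so the bullet is the whole instruction.

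The section then says that "the number of patients with at least one event in each AESI grouping will be reported". It allows a grouping to be built from preferred terms, high level terms, system organ classes, standardized queries, sponsor queries, or a mixture of these. It adds crude rates and, at preferred-term level for the entire treatment period, exposure-adjusted rates with 95% confidence intervals.

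On the protocol side, the summary's safety assessments include injection site reactions, and the adverse-event row of Table 6-1 reads "AEs/ SAEs (including injection site reactions", marked at every visit. Protocol 3.7 states that "Infections, neutropenia and hypersensitivity are important identified risks".

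**The concern.** A two-part topic has a search for one part only. A programmer following the SAP would run the hypersensitivity query and print the result under a label that also promises injection site reactions. A reader of the report would take that row as the count of both.

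Two things are at stake. First, the trial would lack a defined patient-level count of injection site reactions, in a study of a self-injected product whose protocol asks for these events by name. Second, the count for hypersensitivity, which the protocol does list as an important identified risk, would be mixed with any local reactions that the query happens to capture.

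**Working it through.** There is no planned figure to reproduce; the check is of definitions.

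**1. What the row can report.** Let H be the patients with a hypersensitivity event, I the patients with an injection site reaction, and C the part of I whose coded terms fall inside the hypersensitivity query. The row counts the patients in H or C. The documents do not give the query's terms, so take the three possibilities:
- C is empty: the row equals H, and half of its label is never counted.
- C is part of I: the row is neither H nor I.
- C is all of I: the row is H and I together, with neither shown separately.

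In none of these does the row give I by itself. That conclusion does not depend on what the query contains. Whether injection site reactions are undercounted does depend on it, and cannot be settled here.

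**2. What the general tables supply (SAP 2.8.1).** All treatment-emergent events are tabulated by system organ class and preferred term. If two injection-site terms occur in n1 and n2 patients, the number of patients with either lies between max(n1, n2) and n1 + n2, because one patient may have both. The group count therefore cannot be recovered by adding rows.

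**3. What is lost on exposure-adjusted rates.** SAP 2.8.1 gives these for serious events and for events with a frequency above 2%. SAP 2.8.1.1 gives them for AESIs with no threshold. So a non-serious injection-site term at or below 2% gets an adjusted rate only if the hypersensitivity query includes it. The SAP does not state the denominator for the 2%; assume all 352 planned patients:
- 0.02 × 352 = 7.04, so a term seen in 7 or fewer patients stays under the threshold.
- Two such terms with 7 patients each could mean from 7 patients (7/352 = 2.0%) to 14 patients (14/352 = 4.0%), with no adjusted rate for either term.

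Taken by Period 1 group instead, the thresholds are 0.02 × 264 = 5.28 and 0.02 × 88 = 1.76 patients. These figures illustrate the gap; they do not forecast events.

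**4. Exposure to injections (Protocol 3.1.1 and 3.1.2).** Period 1 has one injection at Baseline and at Weeks 1, 2, 3 and 4; Period 2 has two injections at Weeks 8, 12, 16 and 20. A completer receives 5 × 1 + 4 × 2 = 13. Period 1, with 264 against 88 planned patients, is the only placebo comparison. This measures opportunity for local reactions, not the number missed.

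**5. The opportunistic-infection row.** In the infections table this row uses "Opportunistic infections [FINGOLIMOD (CMQ", at the level reserved for sponsor queries. The other rows at that level carry a standard tag, for example "Infections of skin structures [STANDARD] (NMQ". The tag is unusual and unexplained, but the query's subject is the row's subject, and its terms are not given.

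**The case against.** The case against is substantial, and most of it stands.

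- **No event is lost.** Everything is tabulated by arm, system organ class and preferred term, with severity and suspected relationship. A common injection-site term, above 2%, gets an exposure-adjusted rate whether or not it is an AESI. This stands; it leaves the group count and the less common terms.
- **Pooling affects only the grouping count.** The AESI crude rates are shown by preferred term, and the adjusted rates are at that level too, so captured terms can be told apart there. This also stands.
- **Injection site reaction is not a listed risk.** Protocol 3.7 does not name it among the identified risks, the potential risks or the common reactions, while hypersensitivity has a query bearing its own name. True, and it lowers the weight of the point. The SAP nevertheless chose to name the reaction as an AESI topic.
- **The list may be updated and the report will print the searches used.** Updating is tied to accumulating safety data, and printing a search shows what was run. Neither supplies the missing definition.

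A reader might infer that injection site reactions will be understated. The documents do not show this, because the content of the hypersensitivity query is not given. A reader might also infer that opportunistic infections are counted with the wrong list because it carries another product's name. That is not shown either: the tag suggests where the list came from, not that it fails to suit secukinumab. Infections in general also have their own row at system-organ-class level, with separate rows for several infection types.

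**Conclusion.** The point holds in a limited form. SAP 2.8.1.1 names injection site reactions as part of an AESI topic, gives them no search, and reports one pooled patient count from the hypersensitivity query. That rests on the text alone. The size of any undercount is unknown.

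The severity is minor. Only descriptive safety summaries are affected; the primary and secondary efficacy analyses are untouched. What is missing is a patient-level count of injection site reactions, a hypersensitivity count free of them, and adjusted rates for non-serious injection-site terms that are at or below 2% and outside the query.

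The fingolimod-labelled query is not shown to be an error. At most it is a question for the sponsor.

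**What to change.** Before unblinding, replace the combined bullet in SAP 2.8.1.1 with two AESI rows:
- **Hypersensitivity**, identified by the standardized query, with narrow or broad scope stated. Most of the section's other queries state no scope; only the oesophageal candidiasis and infectious pneumonia rows do.
- **Injection site reactions**, identified by the MedDRA injection-site reaction terms, listed in the search table.

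Report for each row the number of patients with at least one event and the exposure-adjusted rate with its 95% confidence interval, by treatment. Separately, ask the sponsor to confirm in one sentence that the fingolimod-labelled opportunistic-infection query applies to secukinumab.

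The cost is SAP wording, one added search definition and one more row per AESI table. No new data are needed, and no dose, schedule or clinical rule changes.
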